- Health care resource utilization and cost inputs were used from published observational studies that were published up to 10 years ago. Revising these estimates with updated RWE could impact the drugs' cost-effectiveness.

The objectives of this observational RWE study are focused on addressing these uncertainties and generating updated cost-effectiveness model inputs. The following research objectives will be addressed:

Primary Objective. Describe baseline demographic characteristics, attack rates, and attack-related medical service utilization among initiators of one of the three treatments for long-term prophylaxis use (Takhzyro, Haegarda, or Cinryze).

- What is the HAE baseline attack rate per month (stratified by severity) in the six months pre-initiation?
- Where is on-demand treatment for acute attacks administered? What is the distribution of specific drugs? How many prescriptions do patients receive?
- For patients with severe attacks, what percent end up hospitalized, and within these patients, what is the utilization of procedures such as cricothyrotomy/tracheotomy, intubation, and artificial respiration?
- What are the costs associated with medical utilization during the acute attack?

Exploratory Objective: Explore attack rates and utilization following long-term prophylaxis initiation.

- What is the severe attack rate per month, post-initiation?
- What percent of patients are attack-free during the follow up period?

- What are the utilization patterns of the prophylactic medications, post initiation?
- What percent of patients receive less frequent dosing for Takhzyro after six months attack free (in line with FDA recommendations)? Do any patients titrate down prior to six months?

5. Research methods

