5.1.1.2 Prophylaxis initiation cohort for evaluation

[figure not shown]
Patients will be eligible to enter the cohort on initiation of Takhzyro, Haegarda, or Cinryze as a prophylactic treatment during October 10, 2008 through October 3rd, 2019 (Figure 1). October 2008 was selected as the start of the study period based on the approval date for Cinryze, the earliest of the medications to be approved. Clinical experts confirmed that 2008 reflects the current treatment paradigm of medications targeting the BK pathway and that all new treatments after 2008 reflect a continual shift away from inferior anabolic androgen therapies. The study period was also selected to maximize sample size for this rare disease.

New use will be defined as no use of Takhzyro or Haegarda, during the 180 days prior (washout period), and no use of Cinryze as a prophylactic treatment during this 180-day washout period. Because Cinryze is used for both acute attacks (off label) and prophylaxis, patients will be excluded based on evidence of prophylactic use of Cinryze (see definition in Annex 2) during the 180 days prior to cohort entry and will be required to have continuous enrollment and evidence of recurring use during the 90 days following cohort entry. Patients receiving other prophylactic treatments (see Annex 1) during the baseline period will also be excluded. Each patient will be included only once, on the first qualifying event. Patients will be required to have at least 180 days of enrollment prior to cohort entry to obtain baseline attack rates.

Using this cohort, we will evaluate baseline outcomes. Patients' demographic characteristics will be assessed at cohort entry. Patients' attack rates, and attack-related medical service utilization and costs will be evaluated.

Note: HAE does not have specific ICD9/10 diagnostic codes. We used initiation of HAE specific treatment to identify patients of interest (i.e., patients with HAE). The method of using HAE treatments to identify HAE patients has been used widely in the literature (Tachdjian 2020, Banerji 2020, [Vande Walle 2018](#)).¹⁻³ In addition, there is no indication that HAE treatments are used off-label for non-HAE patients.

Figure 1: Prophylaxis initiation cohort study design diagram

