5.2.1.5 Costs associated with HAE attacks

Costs will be estimated for HAE attack episodes, by severity and by treatment location (ED only vs inpatient for severe attacks and home versus office for non-sever attacks). Attack costs will be estimated by summing costs across the medical services utilized during an attack, excluding the costs of on-demand therapies, which are included in the cost-effectiveness model separately. Specific outputs will include:

- Outpatient care
 - Cost per attack treated with a home visit for on-demand treatment administration
 - Cost per attack treated with an office visit for on-demand treatment administration
- Cost per attack treated as ED visit
- Cost per attack treated as inpatient hospitalization

If sample size allows, cost analysis will be restricted to most recent years (2017 – 2020) in order to estimate the most timely and relevant costs. This will be a subgroup analysis of the prophylaxis initiation cohort.

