5.2.1.7 Utilization

HAE and all-cause utilization will be estimated for the following:

- Number of home visits
- Number of office visits
- Number of ED visits
- Number of hospitalizations
- Pharmacy utilization
 - HAE on-demand therapy Rx's and total dose
 - HAE prophylaxis therapy Rx's and total dose, including proportion of days covered per label.
 - Other – number of Rx's

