5.4.1.2 Baseline costs (primary objective)

Cost analyses will be based on standard cost amounts reported within the Optum data. Optum's standard costs are based on algorithms that reflect the intensity of care provided, including quantity of services, relative resource costs, and nature of healthcare utilization. Optum's standard costs are an estimate of the allowed amount (i.e., the total cost of the service, and are validated by Optum against the paid amount).¹⁵

All costs will be inflated to 2021 US dollars using Optum's cost factor tables, if 2021 tables are available (typically released in Q2). This method is recommended for Optum data because costs are standardized in multi-year batches.¹⁵ If 2021 tables are not available, costs will be inflated to 2020 US dollars using Optum's cost factor tables and then inflated to 2021 US dollars using the Personal Consumption Expenditure (PCE) price index.¹⁶

Mean values will be reported, along with the standard deviation, median, and inter-quartile range.

To assess sensitivity of results to extreme cost values, additional analyses will be performed where cost values are Winsorized,¹⁷ using the 5th and 95th percentile of the cost distribution as cut points. This procedure involves replacing cost values below the 5th percentile with the 5th percentile value and values above the 95th percentile with the 95th percentile value. Thus, extreme values are pulled in, but the weight on the tails of the distribution is maintained.

If sample size allows, cost analysis will be restricted to most recent years (2017 – 2020) in order to estimate the most timely and relevant costs.

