Annex 3: Results Table Shells

Table 1: Baseline characteristics of patients with HAE

Characteristic	RWE results	Notes	Prior ICER review base case	Prior ICER review source
Mean age			39.63	Banerji et al. 2017, ³⁰ Longhurst et al. 2017, ³¹ Zuraw et al. 2010 ³²
Female, %			68.4%	Banerji et al. 2017, ³⁰ Longhurst et al. 2017, ³¹ Zuraw et al. 2010 ³²
Mean weight, females			76.4	Fryar et al. 2016 ³³
Mean weight, males			88.8	Fryar et al. 2016 ³³
List of top 10 non-HAE therapies (therapeutic class)				

Table 2: Attack rates, utilization, and costs in the six-month baseline period before initiation of prophylaxis treatment

Characteristic	RWE results	Notes	Prior ICER review base case	Prior ICER review source
ATTACK RATES AND TREATMENTS ADMINISTERED				
Mean attack rate per month (HAE-specific severe and non-severe)			3.39	Banerji et al. 2017, ³⁰ Longhurst et al. 2017, ³¹ Zuraw et al. 2010 ³²
Number of patients who are attack free in baseline period before starting prophylaxis therapy		Due to drug indications and health plan requirements, this is expected to be minimal or 0.	-	

Distribution of severe attack free months			-	
Proportion of attacks, by severity				
Severe - HAE specific			-	
Severe - All-cause			-	
Non-severe			-	
Treatment administered – Non-severe attacks				
Self			64.9%	Riedl et al, 2015 ³⁴
Home nurse			13.8%	Riedl et al, 2015 ³⁴
Outpatient			21.3%	Riedl et al, 2015 ³⁴
% of severe-HAE specific attacks resulting in hospitalization			40.9%	Zilberberg et al 2011a ³⁵
% of hospitalized patients receiving cricothyrotomy/tracheotomy			40.0%	Bork et al ³⁶
% of cricothyrotomy/tracheotomy patients who receive artificial respiration			40.0%	Bork et al ³⁶
% of hospitalized patients who are intubated			60.0%	Bork et al ³⁶
% of intubated who receive artificial respiration			26.7%	Bork et al ³⁶
% of attacks treated with these on-demand drugs				Assumption in model
Berinert			25%	
Kalbitor			25%	

Firazyr			25%	
Ruconest			25%	
BASELINE HAE-SPECIFIC COST OUTCOMES				
Costs per home nurse			\$179	Graham et al 2017 ³⁷
Costs per physician office visit			\$266	Graham et al 2017 ³⁷
Costs per ED visit			\$1,796	Zilberberg et al 2011a and 2011b ^{35,38}
Costs per hospitalization			\$5,782	Zilberberg et al 2011a and 2011b ^{35,38}
BASELINE HAE-SPECIFIC UTILIZATION OUTCOMES				
Average number of home visits			-	
Average number physician office visits			-	
Average number of ED visits			-	
Average number of hospitalizations			-	

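### The recent-years restriction is planned for costs only, so setting, drug mix and hospitalization inputs are pooled over 2008–2019 and may be paired with recent unit costs

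*Protocol*

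**What the plan says.** Section 4 lists three uncertainties in the earlier assessment. The third reads: "Health care resource utilization and cost inputs were used from published observational studies that were published up to 10 years ago". It covers utilization as well as cost, and the study is meant to supply updated inputs for the cost-effectiveness model.

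Section 5.1.1.2 defines one cohort for all baseline outcomes, entering "during October 10, 2008 through October 3rd, 2019", with a 180-day baseline before entry. It justifies the 2008 start on two grounds: expert opinion that the treatment paradigm since then is the current one, and the need for numbers in a rare disease.

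The recency restriction appears in Sections 5.2.1.5, 5.2.1.6 and 5.4.1.2, each time for costs. Section 5.2.1.5 says that, where numbers permit, "cost analysis will be restricted to most recent years (2017 – 2020", and adds: "This will be a subgroup analysis of the prophylaxis initiation cohort". Section 5.4.1.2 repeats the restriction with its proviso: "If sample size allows, cost analysis will be restricted to most recent years (2017 – 2020) in order to estimate the most timely and relevant costs".

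Section 5.2.1.7 opens with "HAE and all-cause utilization will be estimated for the following" and sets no calendar limit. Section 5.2.1.8 (hospitalized share, airway procedures) sets none either. Nor do the Table 2 rows in Annex 3 for treatment setting, visit counts and the percentage "of attacks treated with these on-demand drugs". The sensitivity analyses listed in Section 5.4.1.4 vary the attack definition, and none is by calendar period.

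**The concern.** The protocol treats age as a defect of both kinds of input but plans a remedy for one of them. The two are used together. Table 2 lists a cost per home visit, office visit, ED visit and hospitalization, and also the average number of each of those events, the split of settings and the share of severe attacks that end in hospital.

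If the cost restriction is applied, the cost rows describe 2017 onward and the count and share rows describe 2008–2019. The restricted mean total costs of Section 5.2.1.6 would then not reconcile with counts times unit costs, and the model would receive inputs from different periods. If setting, drug mix or hospitalization changed over those years, nothing in the planned output would show it.

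**Working it through.** The protocol gives no patient or attack counts by year, so there is no stated figure to reproduce. What can be checked is the calendar, and how far the answer depends on accrual.

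**Inputs**
- Cohort entry from 10 October 2008 to 3 October 2019, with a 180-day baseline before entry (Section 5.1.1.2).
- Cut at 1 January 2017 (Sections 5.2.1.5, 5.2.1.6 and 5.4.1.2).
- Takhzyro approval on 23 August 2018 (Section 5.1.1.3).
- Protocol date 12 April 2021 (title page).
- Assumption, not in the protocol: r, the ratio of the yearly entry rate in 2017–2019 to that in 2008–2016, varied from 0.5 to 10.

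**Calendar time**
- Earliest baseline day: 10 October 2008 − 180 days = 13 April 2008. This is 13.0 years before the protocol date.
- Latest baseline day: 2 October 2019.
- Baseline span: 4,190 days, of which 3,185 fall before 2017. 3,185 / 4,190 = 76.0%.
- Entry window: 4,011 days, of which 3,005 fall before 2017 and 1,006 from 2017. 3,005 / 4,011 = 74.9%.
- Takhzyro initiators can enter only in the last 407 days: 407 / 4,011 = 10.1% of the window.

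**Entrants**

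Pre-2017 share of entrants w = 3,005 / (3,005 + 1,006 × r).

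| r | w |
|---|---|
| 0.5 | 85.7% |
| 1 | 74.9% |
| 2 | 59.9% |
| 2.99 | 50.0% |
| 4 | 42.8% |
| 5 | 37.4% |
| 10 | 23.0% |

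The break-even is r = 3,005 / 1,006 = 2.99. If entry instead rose linearly from zero over the window, w = (3,005 / 4,011)² = 56.1%.

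**What pooling does**

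For any share-type input, pooled value = w × earlier value + (1 − w) × recent value. The pooled value therefore differs from the recent one by w × (earlier − recent). If attacks are spread over periods as entrants are (a further assumption), the pooled figure misses the recent one by between 23% and 86% of whatever change took place. If nothing changed, it misses by nothing. The protocol has no data on the size of any change.

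**The case against.** The strongest reply is that pooling is a deliberate and disclosed choice. Section 5.1.1.2 gives a clinical reason and a sample-size reason for starting in 2008. A breakdown by period is also an extra analysis of the sort a statistical analysis plan may add. Much of this stands: the all-years cohort is defensible and should be kept, and the text contains no outright contradiction. But the stated clinical reason concerns the class of medication. It does not address where attacks are treated, which on-demand drug is used or how often patients are hospitalized. And the protocol has itself decided that recency matters for one half of a paired set of inputs.

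The mismatch is also conditional. The cost restriction applies only if numbers permit; without it, costs and utilization cover the same years. That stands.

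Some stronger readings are tempting but not supported:

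- A reader might infer that the utilization inputs come mostly from older years. That is shown for calendar days only. With Takhzyro entering late in the window, even accrual cannot be presumed, and above r of about 3 most entrants are recent.
- A reader might take the remark in Section 5.1.1.2 about a continuing shift after 2008 as an admission that setting and drug mix changed. The remark is about moving away from androgens. Annex 1 lists these with prophylactic doses only, and patients on other prophylactic treatments during baseline are excluded.
- A reader might see an error of consequence in the 2020 end year, since no baseline day falls after 2 October 2019. Correcting the label would change no baseline result.
- A reader might conclude that the recent figure should replace the pooled one in the model for every input. The recent subgroup covers only about a quarter of the entry window, so for rare events that is a trade-off. Section 5.4.1.5 also refers to a separate model analysis plan, not at hand, for criteria on using the attack estimates.

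**Conclusion.** The concern holds in a limited form. The protocol names the age of both utilization and cost inputs as a reason for the work, yet it plans a recent-period analysis for costs alone. The utilization inputs are pooled over 2008–2019 with no view by period. About 76% of the possible baseline calendar time precedes 2017. The share of entrants that does is unknown, and runs from about 86% to 23% under assumed entry-rate ratios of 0.5 to 10. If the cost restriction is applied, Table 2 will mix periods. Whether any input is materially biased cannot be said from the protocol, because it gives neither accrual by year nor any evidence of change over time. This is an inexpensive improvement to the plan and does not invalidate it.

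**What to change.** Apply the 2017-onward subgroup already planned for costs to the Table 2 utilization rows as well: treatment setting, on-demand drug shares, visit counts, hospitalized share and airway procedures. Use the same rule for assigning patients to the period as for costs, and the same sample-size proviso. Report the recent column with its denominators beside the all-years column, so that period-matched cost and utilization inputs are available to the model.

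The work is one more column using a subgroup that is already planned. The price is precision: the recent column rests on 1,006 of 4,011 entry days (25.1%, or 2.75 of 10.98 years), and the number of patients left cannot be worked out from the protocol. Cells will be sparse, above all for airway procedures, which are counted only among hospitalized patients. There the all-years figure may have to stand, and the table should say so.

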5.2.1.6 Costs during baseline

Costs will be estimated during a six-month baseline period prior to prophylaxis initiation. Costs will be reported by place of service and by HAE-related health care utilization (minus HAE drug costs) and all-cause utilization. Specific outputs will include:

- Outpatient care
 - Mean total cost of home visits
 - Mean total cost of physician office visits
- Mean total cost of ED visits
- Mean total cost of inpatient hospitalizations

If sample size allows, cost analysis will be restricted to most recent years (2017 – 2020) in order to estimate the most timely and relevant costs. This will be a subgroup analysis of the prophylaxis initiation cohort.

5.2.1.7 Utilization

HAE and all-cause utilization will be estimated for the following:

- Number of home visits
- Number of office visits
- Number of ED visits
- Number of hospitalizations
- Pharmacy utilization
 - HAE on-demand therapy Rx's and total dose
 - HAE prophylaxis therapy Rx's and total dose, including proportion of days covered per label.
 - Other – number of Rx's

5.2.1.8 Hospitalization utilization

For those patients with severe attacks, defined by inpatient hospitalization or ED visit, we will calculate the percentage of patients hospitalized. Of those hospitalized, we will also estimate utilization for the following:

- Percent of patients receiving cricothyrotomy/tracheotomy
 - Percent that also receive artificial respiration
- Percent of patients intubated
 - Percent that also receive artificial respiration

5.3 Data sources

All analyses will be performed using de-identified administrative claims data without access to personal identifying information. Study findings will contain aggregate data only that cannot be used to identify individual patients.

5.3.1.1 Optum's De-identified Clinformatics® Data Mart

Optum's Clinformatics® Data Mart (CDM) is derived from a database of administrative health claims for members of large commercial and Medicare Advantage health plans. The database includes approximately 17-19 million annual covered lives, for a total of over 65 million unique lives over a 9-year period (1/2007 through 12/2019). Clinformatics® Data Mart is statistically de-identified under the Expert Determination method consistent with HIPAA and managed according to Optum® customer data use agreements.^{8,9} CDM administrative claims submitted for payment by providers and pharmacies are verified, adjudicated and de-identified prior to inclusion. This data, including patient-level enrollment information, is derived from claims submitted for all medical and pharmacy health care services with information related to health care costs and resource utilization. The population is geographically diverse, spanning all 50 states.

There are 67,691,644 total patients in the data with events spanned January 1, 2007 through March 31, 2020.

Please see Annex 4 for HAE drug coverage policies for United Healthcare.

5.3.1.2 General notes on administrative databases

Electronic outpatient pharmacy dispensing records are considered accurate because pharmacists fill prescriptions with little room for interpretation, and are reimbursed by insurers on the basis of detailed, complete, and accurate claims submitted electronically.^{10,11} Pharmacy dispensing information is usually seen as the gold standard of drug exposure information compared to self-reported information¹² or prescribing records in outpatient medical records.¹³ Drugs used during hospital stays are not recorded in this data source. Prescribing information based on physician notes may overestimate actual medication use because up to 50% of prescriptions are never filled at the pharmacy.¹⁴

5.4 Statistical analysis

5.4.1.1 Baseline attack rates (primary objective)

Attack rates will be calculated as the total number of attacks in the cohort divided by the number of person-months during baseline (six months prior to initiation of prophylaxis treatment). The rates

and percentages of attacks by severity (severe all-cause, severe-HAE specific, non-severe) will also be calculated for the baseline cohort.

5.4.1.2 Baseline costs (primary objective)

Cost analyses will be based on standard cost amounts reported within the Optum data. Optum's standard costs are based on algorithms that reflect the intensity of care provided, including quantity of services, relative resource costs, and nature of healthcare utilization. Optum's standard costs are an estimate of the allowed amount (i.e., the total cost of the service, and are validated by Optum against the paid amount).¹⁵

All costs will be inflated to 2021 US dollars using Optum's cost factor tables, if 2021 tables are available (typically released in Q2). This method is recommended for Optum data because costs are standardized in multi-year batches.¹⁵ If 2021 tables are not available, costs will be inflated to 2020 US dollars using Optum's cost factor tables and then inflated to 2021 US dollars using the Personal Consumption Expenditure (PCE) price index.¹⁶

Mean values will be reported, along with the standard deviation, median, and inter-quartile range.

To assess sensitivity of results to extreme cost values, additional analyses will be performed where cost values are Winsorized,¹⁷ using the 5th and 95th percentile of the cost distribution as cut points. This procedure involves replacing cost values below the 5th percentile with the 5th percentile value and values above the 95th percentile with the 95th percentile value. Thus, extreme values are pulled in, but the weight on the tails of the distribution is maintained.

If sample size allows, cost analysis will be restricted to most recent years (2017 – 2020) in order to estimate the most timely and relevant costs.

5.4.1.3 Exploratory Follow-up descriptive analyses

Due to the small sample size, there is a lack of power to complete a formal pre/post analysis to detect a meaningful difference in attack rates. Thus, our follow-up analysis will be descriptive.

In the follow up period, we are interested in exploring the frequency of attacks after initiation of prophylaxis therapy, understanding utilization, and determining how many months patients were attack free after initiation. Follow up attack rates will be stratified by drug (Takhzyro, Haegarda, and Cinryze) and we will focus on severe attacks only. We will explore the following:

- Adherence to prophylaxis therapy
- Switching behavior between the three prophylaxis drugs
- Attack rates, including attack-free months

